6.5.1 Removal from Trial

While subjects will be encouraged to continue participation in the study for safety follow-up, subjects **MUST** be discontinued from the study for the following reasons:

1. Pregnancy within 1 month before or 4 months after study regimen administration (NOTE: All FCBP should be instructed to contact the investigator immediately if they suspect they might be pregnant [e.g., missed or late menstrual period] at any time during study participation.)
2. Termination of the study for safety

3. Imprisonment or the compulsory detention for treatment of either a psychiatric or physical (e.g., infectious disease) illness
4. Other

6.5.2 Removal from Study Drug

While subjects will be encouraged to continue participation in the study for safety and survival follow-up, subjects **MUST** be discontinued from receiving further study drug for the following reason:

- Progressive disease by RECIST v1.1 criteria
- Withdrawal of informed consent from study treatment
 - Subject will continue to be followed for imaging and quality-of-life assessment
- Any clinical AE that meets treatment discontinuation criteria in section 5.6 or any other reason that, in the opinion of the investigator, indicates that continued dosing on the study is not in the best interest of the subject
 - Subject will continue to be followed for imaging and quality-of-life assessment

Subjects will be permitted to continue study drug if the RECIST v1.1 criteria for PD are met provided they meet all the following criteria:

- Evidence of clinical benefit as assessed by the investigator
- Absence of symptoms and signs (including worsening of laboratory values) indicating unequivocal progression of disease
- No decline in ECOG performance status that can be attributed to disease progression
- Absence of tumor growth at critical anatomical sites (e.g., leptomeningeal disease) that cannot be managed by protocol-allowed medical interventions
- Subjects for whom approved therapies exist must provide written consent to acknowledge deferring these treatment options in favor of continuing study treatment at the time of initial apparent progression. Study treatment will be discontinued upon commencement of subsequent systemic anti-tumor therapy.

No unblinding will be permitted for subjects who continue study treatment beyond progression.

6.6 Appropriateness of Measurements

The measurements of efficacy and safety in this study are standard measurements widely used and generally recognized as reliable, accurate, and relevant. The safety measurements evaluated in this study are those used in most clinical studies, including the assessment of AEs.

7.0 PLANNED STATISTICAL METHODS

7.1 Determination of Sample Size

A total of 248 subjects will be randomly assigned in a 1:1 ratio such that 124 subjects will be included in each of the 2 treatment arms. The study is powered at 90% with 179 death events required to detect a HR of 0.59, which corresponds to a 41% reduction in the risk of death, and an approximately 69% increase in median survival compared with a placebo median survival of 20 months, and uses a 1-sided log-rank test, with an alpha of 0.0125, a 1:1 randomization ratio, and an interim OS non-binding futility analysis with boundary of HR = 1.0 at 67% of information time (120 death events from the 179 required death events for the final OS analysis). A total of 248 subjects will yield the 179 events required, under the assumption of 24 months for enrollment (25% of subjects enrolled in the first year and 75% of subjects enrolled in the second year) plus 42 additional months of follow-up.

With 141 PFS events, the study is powered at 90% to detect a HR of 0.55, which corresponds to a 45% reduction in the risk of PFS events (either disease progression or death), and an approximately 82% increase in median PFS compared with a placebo median PFS of 4 months, and uses a 1-sided log-rank test, with an alpha of 0.0125, and a 1:1 randomization ratio.

7.2 Analysis Sets

For the purpose of statistical analysis, there are 3 analysis sets: Intent-to-Treat set (ITT), Efficacy Evaluable set (EE), and Safety set.

- The ITT set consists of all subjects randomized. All analyses of this set will be based on the randomized treatment arm to which the subjects are assigned. Efficacy analyses performed in the ITT set will be considered to be the primary indicator of efficacy.
- The EE set consists of all subjects without major protocol violations, who have received at least 1 dose of study drug, and have the baseline and at least 1 post-baseline tumor assessments available. The EE set will be analyzed according to the treatment received. Efficacy analyses performed in the EE set will be considered to be supportive.
- The Safety set consists of all subjects taking any amount of study drug. The Safety set is the primary set for safety analyses including AEs and clinical laboratory data. Study treatment exposure also will be summarized using the Safety set. Efficacy analyses performed in the Safety set will be considered to be supportive.

7.3 Demographics and Baseline Characteristics

Subject disposition and characteristics including demographics, disease duration and stage at Screening, and relevant medical history will be summarized for the purpose of characterizing the subject population by treatment arm and establishing baseline comparability of the randomized treatment arms.

7.4 Primary Endpoints

- PFS, defined as the time from randomization to the investigator-determined (using RECIST v1.1) date of disease progression or death
- OS, as the time from randomization to the date of death

7.5 Secondary Endpoints

- TTNT
- DMFS
- ORR, defined by RECIST v1.1
- Safety and tolerability
- QoL, using the EQ-5D-5L for subjects ≥ 18 years of age or using the EQ-5D-Y for subjects 12 to < 18 years of age

7.6 Exploratory Assessments or Analyses

- Intratumoral and peripheral blood anti-NY-ESO-1 immune changes

7.7 Efficacy Analysis

7.7.1 Primary Efficacy Analyses:

The 2 primary efficacy endpoints of PFS and OS will be compared between CMB305 and placebo. Overall survival is defined as the time from randomization to the date of death.

Progression-free survival by investigator's assessment is defined as the time from randomization to the investigator-determined (using RECIST v1.1) date of disease progression or death. Radiographic images will be collected and assessed using RECIST v1.1 until the time the subject begins a new line of treatment.

For the purpose of PFS analysis, any one of the following events, whichever occurs first, will be used:

- Disease progression per RECIST v1.1 (See Appendix 1 [Table 7 \[Eisenhauer 2009\]](#))
- Symptomatic deterioration (global health deterioration) as described by RECIST v1.1
- For subjects with NED at time of randomization, any new malignant lesion that occurs after randomization per RECIST v1.1 (See Appendix 1 [Table 8](#))

Otherwise, subjects who do not have disease progression or have not died will be censored at the date when the last tumor imaging assessment determines a lack of progression. If a subject begins a new anti-cancer therapy or has radiotherapy, surgery, or other local regional therapy at a lesion site prior to documented progression, the subject will be censored at the last assessment where the subject was documented as progression free prior to the intervention. For subjects with NED at study entry, the appearance of a new malignant lesion as per RECIST v1.1 is defined as an event of progression for the purpose of PFS analysis. Subjects with 2 or more missing

response assessments (except for subjects with symptomatic deterioration) prior to a visit with documented progression (or death) will be censored at the last visit where the subject was documented to be progression free. PFS, by investigator's assessment, will be the primary PFS analysis. PFS by independent radiological review will be the supportive analysis.

The null hypothesis of no difference in OS/PFS between CMB305 and placebo, will be tested using a stratified log-rank test stratified by: disease status at screening (locally advanced unresectable versus metastatic), tumor response during screening (PR/SD versus CR/ NED), and by baseline presence of anti-NY-ESO-1 antibody (yes versus no)).

The null hypothesis will be rejected, and it will be concluded that OS/PFS on CMB305 is superior to that on placebo in subjects with synovial sarcoma if the 1-sided p value at the final analysis for the stratified log-rank test is less than the pre-specified alpha of 0.0125 as discussed in [Section 7.10](#), Multiplicity. The associated HR and its 2-sided 97.5% and 95% CI will be provided using the stratified Cox proportional hazard model. The Kaplan-Meier curve will summarize OS/PFS graphically by treatment arm. Tabular summaries of the Kaplan-Meier curves, including the median, will be provided by treatment. The 1-year and 18-month OS/PFS rate will be provided by treatment. The final PFS analysis will be conducted when a total of 141 PFS events occur. The final OS analysis will be conducted when a total of 179 deaths occur.

A pre-planned sensitivity analysis will be performed based on the number of cycles and type of prior therapy (neoadjuvant/adjuvant chemotherapy and surgery and/or radiotherapy).

7.7.2 Secondary Efficacy Analyses:

The secondary efficacy endpoints of TTNT, DMFS, ORR and QoL using the EQ-5D-5L or EQ-5D-Y will be compared between treatment arms.

The secondary efficacy endpoints will only be evaluated if at least one of the primary efficacy endpoints demonstrates superiority for CMB305 over placebo. Furthermore, to control the overall family-wise type I error rate at 1-sided $\alpha = 0.025$ for the secondary efficacy endpoints, the secondary efficacy endpoint of TTNT will be tested first at 1-sided alpha of 0.025. DMFS will be tested at 1-sided alpha of 0.025 only if TTNT shows significant improvement.

7.7.2.1 Time to Next Treatment

Time to next treatment is defined as the time from randomization to start of post-study treatment anti-cancer therapy. Subjects who do not start post-study treatment anti-cancer therapy will be censored at their last known date of being alive. TTNT will be analyzed using the same methods described for OS/PFS. In the event that the percent of subjects with competing events in either arm exceeds 3%, the cumulative incidence estimates, and Gray's test will be the main TTNT comparison between the treatment arms.

7.7.2.2 Distant Metastasis-Free Survival

Distant metastasis-free survival is defined as the time from randomization to evidence of a new distant metastasis not documented at time of randomization. DMFS will be analyzed using the same methods described for OS/PFS. In the event that the percent of subjects with competing events in either arm exceeds 3%, the cumulative incidence estimates, and Gray's test will be the main DMFS comparison between the treatment arms.

7.7.2.3 Other Secondary Efficacy Endpoints

ORR defined by RECIST v1.1 will be summarized by the number and percent of subjects who achieve a CR or PR based on the investigator's assessment. ORR will be compared between treatment arms using a logistic regression.

QoL (EQ-5D-5L or EQ-5D-Y) scores will be compared between the treatment arms using a mixed model.

7.8 Safety Analysis

Safety will be assessed primarily based on reported AEs. A TEAE is an AE with an onset on or after the initiation of study treatment, or a pre-existing condition that worsens after initiation of study treatment (i.e., increase in severity). Medical events of interest, immune-mediated events, and AEs that occur more than 30 days after the last dose, and that are deemed as related to the study drug, will be included as TEAEs. TEAEs occurring from the time of the first dose through 30 days after the last dose of the study drug and medical events of interest, immune-mediated events and related AEs will be summarized. All AEs will be coded using the Medical Dictionary for Regulatory Affairs® (MedDRA v20.0 or newer). TEAEs will be tabulated by system organ class, preferred term, by treatment, and will be further categorized by NCI-CTCAE (v4.03 or newer) grade, and by relationship to the study drug. Clinically significant laboratory abnormalities, as measured by either the local or central laboratory, will be reported as AEs. The incidence for each AE will be provided as the total number of subjects that experience the AE, as well as the percentage of the population that this represents. If an AE is reported more than once during treatment for a given subject, the worst grade of severity and the most conservative relationship will be presented in the summary tables.

AEs will also be listed for individual subjects, along with information regarding onset, duration, grade, relationship to the study drug, and outcome. AEs that lead to withdrawal from the study treatment will be listed and summarized. Tabulations and listings of SAEs and deaths also will be generated.

Treatment exposure will be provided by treatment arm. The number of CMB305 or placebo injections, duration of exposure, and number of subjects with dose reductions/interruptions will be summarized by treatment arm based on the Safety set.

Laboratory values measured by the central laboratory will be used in the analysis of laboratory toxicities and will be defined based on universal normal ranges and NCI-CTCAE, Version 4.03 or newer. The number and percentage of subjects will be summarized by grade using the most severe grade by treatment arm. Clinically significant changes in laboratory values will be summarized by treatment arm. Laboratory values will be listed, with grade 3 or 4 values flagged.

All concomitant medications and prior medications will be coded to therapeutic drug classes and generic drug names using the World Health Organization (WHO) Drug Classification. The incidence of prior and concomitant medication usage will be summarized by treatment arm, by therapeutic drug class, and generic drug names.

7.9 Exploratory Analysis

The baseline anti-NY-ESO-1 immune response and histologic and molecular changes in peripheral blood and tumor tissue and their association with clinical outcomes will be explored. In addition, a relationship between an induced anti-NY-ESO-1 immune response as well as tumor tissue changes during study treatment and clinical outcomes will be evaluated using peripheral blood and tumor tissue biopsies collected during study treatment at select sites.

7.10 Multiplicity

The study is to be conducted with PFS and OS as 2 primary endpoints with the goal of a regulatory approval based on PFS or OS. The overall type I error probability is specified to be 1-sided 0.025 with success for either of the 2 primary endpoints defining study success using the Bonferroni method to specify that each endpoint will be evaluated using a type I error probability of 1-sided 0.0125 in order to protect the overall type I error.

7.11 Data Monitoring Committee and Interim Analysis

A data monitoring committee will be established with the responsibility of safeguarding the interest of study subjects and maintaining the overall integrity of the study. The DMC will review safety data periodically during the study as described under [Section 8.17](#) (Data Monitoring Committee) of this protocol and will evaluate the results of final PFS analysis and a planned interim OS analysis to assess futility with the possibility of a recommendation for stopping the study early because of futility. The OS non-binding futility boundary is set to be $HR = 1.0$. It will be conducted at 67% of information time (120th death event from the 179 required death events for final OS analysis). If deemed necessary by the DMC, unblinded data may be reviewed on a case-by-case basis. The sponsor will remain blinded to study treatment until either 1 of the 2 primary endpoints is met or until the study has been stopped early. Details of DMC function will be governed by a DMC Charter developed by the sponsor and accepted by DMC members.

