5.2 Treatments Administered

LV305 will be administered on Days 1, 22, 50, and 78. For each day of administration, the LV305 daily dose of 4×10^{10} vg will be given as 4 separate 1-mL SC injections of 1×10^{10} vg/mL administered preferably to a separate extremity (upper or lower limb [or stump if subject had prior resection]). If injection to a separate extremity is not feasible, then each SC injection should be at least 3 cm from the neighboring injection site of the same extremity.

G305 is an admixture of NY-ESO-1 and GLA-SE described in the Pharmacy Manual. G305 will be administered via IM injection in the anterior upper thigh or deltoid region on Days 36, 64, and 92, and then at 8-week intervals up to 1 year or until investigator-determined PD (using RECIST v1.1) is documented or unacceptable toxicity, whichever occurs first. The quantity of

recombinant NY-ESO-1 protein is fixed at 250 µg/dose, and the dose of GLA-SE will be 5 µg of GLA in a 2% oil-in-water emulsion. The limb or stump used for injection will be alternated with each treatment.

Three placebos (fully matched to characteristics of LV305, the NY-ESO-1 protein, and GLA-SE) will be provided for this study and will be administered on the same schedule and by the same route as the corresponding experimental therapy components to ensure that the sponsor, site personnel (including pharmacist), and subjects remain blinded to study drug for the duration of the study.

[figure not shown]
Matching placebo for LV305 will be administered by the same route and on the same days as LV305; matching placebos for G305 will be mixed per the Pharmacy Manual in the same manner as the product G305 and then administered by the same route and on the same days as G305.

Full details on the administration of CMB305 and matching placebo will be provided in the Pharmacy Manual provided to study sites.

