**Figure 1 CMB305 or Matching Placebo Dosing Regimen**

LV305 or matching placebo is administered as 4 separate 1-mL SC on Days 1, 22, 50, and 78, each preferably administered in a separate upper or lower limb (or stump if the subject has had a resection), or administered at least 3 cm from the neighboring injection site if on the same limb/stump.

G305 or matching placebo is administered IM on Days 36, 64, and 92, and then at 8-week intervals up to 1 year or until investigator-determined PD (using RECIST v1.1) is documented or unacceptable toxicity, whichever occurs first..

Three placebos (fully matched to characteristics of LV305, the NY-ESO-1 protein, and GLA-SE) will be provided for this study and will be administered on the same schedule and by the same route as the corresponding experimental therapy components to ensure that the sponsor, site personnel (including pharmacist), and subjects remain blinded to study drug for the duration of the study.

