### 7.4 Interim Analyses and Data Monitoring

A data monitoring committee will be established with the responsibility of safeguarding the interest of study subjects and maintaining the overall integrity of the study. The DMC will review safety data periodically during the study as described under Section 8.17 (Data Monitoring Committee) of the protocol and will evaluate the results of final PFS analysis and a planned interim OS analysis to assess futility with the possibility of a recommendation for stopping the study early because of futility. The OS non-binding futility boundary is set to be HR = 1.0. It will be conducted at 67% of information time (120th death event from the 179 required death events for final OS analysis). If deemed necessary by the DMC, unblinded data may be reviewed on a case-by-case basis. The sponsor will remain blinded to study treatment until either

1 of the 2 primary endpoints is met or until the study has been stopped early. Details of DMC function will be governed by a DMC Charter developed by the sponsor and accepted by DMC members.

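### The plan lets sponsor blinding lapse once PFS is met, when only about 27% of the 179 OS deaths are expected, while other sections of both documents promise or imply sponsor blinding throughout

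*Protocol*

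**What the plan says.** Two sets of statements bear on how long the sponsor stays blinded.

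*Blinding may end early.* Protocol 7.11 reads: "The sponsor will remain blinded to study treatment until either 1 of the 2 primary endpoints is met". An early stop of the trial is the other condition that ends the commitment. The synopsis repeats this. SAP 7.4 carries the same rule, opening with "The sponsor will remain blinded to study treatment until either" and naming the same two conditions.

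*Blinding does not end early.* Protocol 5.2 says the matched placebos are there "to ensure that the sponsor, site personnel (including pharmacist), and subjects remain blinded to study drug for the duration of the study". SAP 3.1.2 repeats this under its Figure 1; the sentence names the sponsor and ends "subjects remain blinded to study drug for the duration of the study". Protocol 5.5 and SAP 3.3.2 list as blinded the subjects, investigators, site personnel, central imaging readers, the sponsor, and sponsor representatives who conduct or manage the study. The only exception given there is emergency unblinding. Neither section mentions an end at PFS success.

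OS remains confirmatory after the PFS analysis. Under Protocol 7.10, "each endpoint will be evaluated using a type I error probability of 1-sided 0.0125". Protocol 7.7.1 puts the final PFS analysis at 141 events and the final OS analysis at 179 deaths, and 7.11 puts a non-binding OS futility look at 120 deaths. SAP 7.3 adds a Hochberg step that uses the final OS p value together with the PFS p value.

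**The concern.** PFS reads out long before OS matures. A rule that releases the sponsor from blinding when the first primary endpoint is met therefore releases it while the second is still accruing most of its events. Neither document says who may see subject-level assignments at that point, or that the team running the study stays blinded until OS is final.

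What is at stake is the set of decisions that stay in sponsor hands during OS follow-up:

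- The sponsor may ask for more frequent survival-status updates (Protocol Table 2 footnotes and 6.5). These affect when deaths are captured and where living subjects are censored.
- The clinical study team defines the major deviations that remove subjects from the EE set and reviews them quarterly (SAP 8.1.2).
- The SAP may be revised during the study (SAP 1). It leaves some choices open, such as the piecewise Cox cut points (given only as an example, SAP 8.2.2.2) and the covariates of the multivariable models (SAP 8.2.2.3).
- The futility boundary is non-binding, and follow-up may end when the sponsor notifies sites of study closure (Protocol 3.1.5).

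Each of these is open to bias, or to a charge of bias, if the people involved know the assignments.

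**Working it through.** **Inputs (Protocol 7.1 and 7.7.1).** For OS: "The study is powered at 90% with 179 death events required to detect a HR of 0.59", "compared with a placebo median survival of 20 months". For PFS: 141 events, 90% power, HR 0.55, placebo median 4 months. Each test uses 1-sided 0.0125. There are 248 subjects, 1:1. Enrollment takes 24 months, 25% in year 1 and 75% in year 2, followed by 42 months of follow-up.

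**Step 1: reproduce the plan's event counts.** Schoenfeld's formula is d = 4(z₀.₉₈₇₅ + z₀.₉₀)² / (ln HR)², with 2.2414 + 1.2816 = 3.5230.

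- OS: 4 × 3.5230² / (ln 0.59)² = 178.3, so 179. This matches the plan. Power at 179 is 90.1%, and still 90.1% with the HR = 1.0 look at 120 deaths.
- PFS: 4 × 3.5230² / (ln 0.55)² = 138.9, so 139 against 141 stated. Power at 141 is 90.5%.

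**Step 2: timing model.** Assume exponential times, no dropout, and uniform accrual within each year. Each arm of 124 enrolls 31/12 per month in year 1 and 93/12 per month in year 2. For an accrual segment from a to b (b capped at T) at rate r, the expected events by calendar month T are

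r × { (b − a) − [e^(−λ(T−b)) − e^(−λ(T−a))] / λ }.

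The hazards per month are: PFS placebo ln 2/4 = 0.1733, and CMB305 0.55 times that = 0.0953; OS placebo ln 2/20 = 0.0347, and CMB305 0.59 times that = 0.0204.

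**Step 3: check the model against the plan.** At month 66 (24 + 42) it gives 102.3 + 79.9 = 182 deaths, and it reaches 179 at month 64.1. That agrees with the plan's claim that 248 subjects yield 179 deaths in this time.

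**Step 4: OS maturity at the PFS analysis.** PFS events reach 80.5 + 60.5 = 141 at month 23.6.

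- Enrolled by then: 62 + 186 × 11.6/12 ≈ 242 of 248. About 242 − 141 = 101 of them are still free of a PFS event.
- Expected deaths: 30.0 (placebo) + 19.2 (CMB305) = 49.2, and 49.2/179 = 27.5%.
- Still to come: 179 − 49.2 ≈ 130 deaths (73%), over 64.1 − 23.6 ≈ 40 months. The 120th death falls at about month 40.1, so the futility look also lies ahead.

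**Step 5: sensitivity.** Censoring rates and alternative PFS medians are assumptions, not figures from the documents.

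| Case | Month of 141st PFS event | Deaths | Share of 179 |
|---|---|---|---|
| Design assumptions | 23.6 | 49.2 | 27% |
| PFS effect as planned, no OS effect | 23.6 | 59.9 | 33% |
| No effect on either endpoint | 22.2 | 51.1 | 29% |
| Uniform accrual over 24 months | 21.0 | 51.7 | 29% |
| PFS censoring 10% per year | 24.0 | 51.2 | 29% |
| PFS censoring 20% per year | 24.5 | 53.6 | 30% |
| PFS censoring 40% per year | 25.8 | 60.8 | 34% |
| Placebo median PFS 6 months | 26.3 | 63.0 | 35% |
| Placebo median PFS 8 months | 29.2 | 76.9 | 43% |

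In every case fewer than half of the deaths have occurred, and the 120-death look has not been reached.

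**Step 6: does any rule of precedence settle the conflict?** SAP 9 says the SAP prevails over the protocol. That does not help, because the SAP contains both statements (3.1.2 and 7.4).

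**The case against.** Several points on the other side are sound and limit the concern.

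- *Section 7.11 does not order unblinding.* A reader might infer that the whole sponsor is unblinded the moment PFS is met. The sentence only sets when the commitment to blinding lapses. It does not say that assignments are released, or to whom.
- *The conduct team is covered elsewhere.* It would be wrong to say that nothing keeps it blinded. Protocol 5.5 and SAP 3.3.2 name it. What is missing is a sentence that reconciles those sections with 7.11.
- *Sites and subjects are not affected.* A reader might infer that the choice of next treatment would differ by arm. Investigators and subjects make that choice, and 7.11 concerns only the sponsor. Protocol 3.1.3 bars crossover before study closure, and 6.5.2 bars unblinding of subjects treated beyond progression.
- *OS is objective.* Death from any cause leaves little room for differential adjudication. Survival status is scheduled every 3 months and may come from any source.
- *TTNT and DMFS.* A reader might infer that these tests are exposed too. The documents set no later analysis time for them. Their gate opens once one primary endpoint succeeds, so they may be tested at the PFS analysis.
- *The DMC charter is not public.* It may already restrict access.
- *Approval on PFS alone is a stated goal,* so some sponsor access to PFS results fits the design.

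These points narrow the route to harm and make the scenario conditional on PFS success, but they leave the contradiction in place. Nor do they supply a rule for who may see assignments while OS is open. The scenario is not remote either: the plan gives PFS 90% power under its own assumptions.

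**Conclusion.** The concern holds in a limited form. The two documents contradict themselves on how long the sponsor stays blinded. Read as written, 7.11 permits sponsor unblinding when about 49 of 179 deaths (27%) are expected, with about 130 deaths, about 40 months and the futility look still to come. The 27% appears nowhere in the documents. It rests on the plan's medians, hazard ratios and accrual, exponential times, no dropout, and PFS success at the 141-event analysis. The alternatives tried give up to 43%.

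The consequence is a risk to the integrity and credibility of sponsor-controlled conduct during OS follow-up. It is not a demonstrated bias in OS, and the documents do not support a claim that the type I error is inflated. OS is nevertheless a live confirmatory test at that point. Under SAP 7.3, a PFS p value below 0.0125 even allows OS to be declared significant at p below 0.025. The matter needs settling before the PFS readout, because a broken blind cannot be restored.

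**What to change.** Reconcile the synopsis, Protocol 5.2, 5.5 and 7.11, and SAP 3.1.2, 3.3.2 and 7.4, and carry the same rule into the DMC charter. Suggested wording:

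> If the PFS analysis is positive, subject-level treatment assignments are released only to a restricted group that prepares the PFS reporting. The sponsor's study-conduct team, the sites and the subjects remain blinded at subject level until the final OS analysis or study closure. Emergency unblinding is unaffected.

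The text should also name who belongs to the restricted group, and state that its members take no part in survival follow-up, deviation classification, SAP revision or decisions on the OS futility result. Other access arrangements would serve if they keep those functions blinded.

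The cost is a change of wording in three documents and a small access-control burden, which should fit within existing staff, although the documents give no staffing figures to confirm that. Alpha, event targets, sample size and analysis timing do not change.
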